## **1 Protocol Summary**

The overall aim of this study is to increase use of intrauterine contraception (IUC) after medical abortion as IUC post abortion lowers rates of abortions and repeat abortions.(1-4) Our hypothesis is that immediate insertion of IUC after medical abortion results in higher use of IUC at six months post abortion compared to the current routine of delayed IUC insertion at 2-4 weeks post abortion.

Today 90 percent of terminations of pregnancy are medical abortions. Approximately 33 000 medical abortions are performed in Sweden each year and 20-30 percent of these women opt for IUC as post abortion contraception. Thus, the results of this study potentially affect at least 6600-9900 women every year in Sweden alone. A disadvantage with medical abortion compared with surgical abortion is the standard practice of delayed insertion of IUC. It has been shown that 42 percent of women scheduled for delayed insertion after surgical abortion did not return for the follow up and IUC insertion.(5) This problem is common also in medical abortion practice. Immediate insertion could lead to insertion rates close to 100 percent. However, this practice has not been studied for medical abortion.

The background for this trial is the belief that a higher rate of insertion of IUC, perhaps close to 100 percent, within 48 hours after medical abortion, can compensate more than well for a potentially higher rate of expulsion at immediate insertion. A clinically significant difference in IUC use at six months following the medical abortion of at least 20 percent is expected.

This large multicenter, randomized, patient centered clinical trial will investigate the effectiveness, feasibility, continued use, safety and acceptability of immediate insertion of intrauterine contraception within 0-48 hours after a completed medical abortion when compared to delayed IUC insertion at 2-4 weeks post abortion which is current practice.

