### **Variables and measures**

Primary outcome measure:

- Use of IUC at 6 months post insertion evaluated by telephone follow-up and through patient records. This will be evaluated as the proportion of women in each gestational strata (use of IUC versus no use of IUC).

Secondary outcome measures:

- Difference in the proportion of women who successfully have the IUC inserted (success versus failure),
- Expulsion rate during 12 months following insertion in both groups evaluated by telephone/email follow up at 3, 6 and 12 months post abortion (complete, partial or no expulsion. The exact day of expulsion will be noted to determine the risk of expulsion as a function of time post insertion),

- Continued use of IUC at 3, 6 and 12 months post insertion evaluated by telephone follow-up (continued use/voluntary discontinued use, involuntary discontinued use including expulsions etc) reasons for discontinuation will be recorded and subsequent use of other contraceptive methods will be noted)
- Ease of insertion according to health care provider (judged as very easy, moderately-, or very difficult)
- pain at time of insertion (women will indicate the pain before insertion, at placement of tenaculum, sound and IUC by putting a vertical mark on a 10 cm long horizontal line with a Visual Analogue Scale (VAS) from 0, indicating no pain to 10 indicating worst imaginable pain. Result will be noted in millimeters and entered into case report forms).
- Post-abortion bleeding (number of days of fresh bleeding and spotting after the abortion)
- Reasons for non-attempted insertion of IUC (change of mind, heavy bleeding, not coming for insertion, staff being unavailable etc),
- Complications (adverse events (AE) and serious AE) bleeding requiring any treatment, uterine perforations and cervical tears, infection requiring treatment with antibiotics, hospitalization for any reason, surgical procedures due to heavy bleeding, incomplete abortions, prolonged bleeding or patient request,
- Pregnancies occurring during the 12 month follow-up (planned and unplanned, wanted and unwanted, pregnancy outcomes- ectopic, miscarriage, abortion, molar, kept pregnancy),
- Acceptability of immediate and delayed insertion of IUC by asking women if they would recommend the procedure to a friend (yes/no, asked at the time of insertion and at the 3, 6 and 12 month follow up),
- Acceptability of IUC as post abortion contraception- evaluated as above,

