- The proportion of surgical procedures in total and for each study site (type of procedure, reasons therefore- infection, retained products of conception, prolonged bleeding etc).

Follow up for all women will be by telephone (call) and/or email (by special invitation to a link) with a structured questionnaire with multiple choice questions at 3, 6 and 12 months post abortion when primary and secondary objectives will be reported as described above. Women will answer questions regarding: post abortion bleeding and current bleeding pattern, continued use of IUC/other use of contraception, reasons for non-use of IUC (expulsion, never inserted- reasons, extracted- reason for this), complications (expulsion, infection, surgical intervention

etc), satisfaction with their current contraceptive method and experience of unintended/intended pregnancy and the results of these pregnancies. In addition, patient records in both groups will be reviewed after 6 months in order to extract information concerning possible extra visits related to the abortion or IUC related complications.

Data will be recorded on individual printed case report forms (CRFs), after which they will be entered via a digital case report form (eCRF) using a centre-specific module. Data quality will be assured by both computer-generated verification of consistency and by manual review at monitoring visits. E-CRFs from all sites can only be accessed by the PI and will be transferred into a database. The database will contain information on demographic variables, type of IUC inserted and sound measurement in addition to the variables above.

The end of study is defined as completion of the last visit of the last subject. The sponsor and the investigators reserve the rights to discontinue the study at any time for safety reasons or other reasons jeopardizing the justifications of the study.

An interim analysis of results will be performed when 50 percent of women have been recruited in any gestational strata. If expulsion rates exceed 20 percent or if acceptability rates are below 50 percent by the 3 month follow up the study will be stopped. If the study is prematurely terminated or suspended, the investigator should promptly inform the participants and assure appropriate therapy and follow-up.

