## ***6.2 Exclusion criteria***

- Contraindication for medical abortion or
- Contraindication for IUC (contraindications may be present for LNG-IUSs but the woman may still choose a Cu-IUD and thereby enter the study),
- inability to give informed consent.
- Septic abortion
- Known hypersensitivity/allergy to levonorgestrel or any of the substances added to the LNG-IUS
- Known abnormal uterine cavity
- Chorioamnionitis
- Abortion associated bleeding > 1000ml
- Uterine atony postabortion
- Placental retention
- Therapeutic antibiotic treatment during abortion, (antibiotics used only as prophylaxis is accepted)
- History of breast cancer
- If any of the following conditions are present an individual evaluation and decision must be done before inclusion: pelvic or genital infection, cervicitis, immunocompromised women, untreated cervical dysplasia, neoplasia in cervix or uterus, acute liver disease or hepatic neoplasia, migraine or other very severe headache, icterus, high uncontrolled blood pressure, serious arterial disease i.e. stroke or myocardial infarction, acute venous thrombosis

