A sensitivity analysis will be performed on a strict ITT-population consisting of all randomized women having had medical abortion. In this analysis it is required to impute the outcome for women lost to follow up.

- Secondary efficacy outcomes:

1. Abortion rate as difference in proportion of individuals in each group at 3, 6 and 12 months,

Since both the primary outcome and this outcome involve data from different time-points several tests can be performed. In order to reduce the risk for type-I error each research question will be addressed with a global test including all available time-points first, before studying individual time-points. The data has a repeated-measure structure with a dichotomous outcome and most likely more observations available for early time-point compared to later time-points. To properly handle this data-structure we will use a multivariate permutation test based on a Fisher's combination function of individual  $p$ -values from time-specific tests (Fisher's exact test). If this global test is non-significant no individual time-points will be considered significant

2. Difference in the proportion of women who successfully have the IUC inserted (success versus failure),

Analyzed by Fisher's exact test.

- Secondary safety outcomes

1. rate of complications such as expulsions, perforations, infections. (Fisher's exact test)
2. Length of post abortion bleeding (difference in mean number of days in groups and per IUC use (hormonal/copper). Analyzed by T-test or Mann-Whitney U-test depending on the observed distribution (normal or skewed).
3. Pain at insertion on a VAS. Analyzed by Student's t-test

These secondary analyses concern safety where it is not sensible to adjust for multiple testing. The adjustments (with e.g. Bonferroni) increases the risk for type-II errors. As safety issues are very important we do not wish to increase the risk for type-II errors. Moreover, the analyses are listed under secondary endpoints so this implies that the results should be interpreted with more caution compared to the primary result.

- Secondary acceptability outcomes
  1. preferred method: immediate or delayed and if they would recommend their timing of insertion to a friend (yes/no). Analyzed by multivariate logistic regression with group, demographic variables and type of IUC (hormonal/copper) as explanatory variables.

Secondary analyses will be performed on all women with available data.

- Interim analysis:

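### The acceptability model adjusts for type of IUC, and unless the intended type is recorded at entry this drops never-inserted women, most of them in the delayed arm

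*Protocol*

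**What the plan says.** Section 17.1, under the secondary acceptability outcomes, has two items: the timing the woman prefers, and whether she would recommend her own timing to a friend. Both go into a logistic regression "with group, demographic variables and type of IUC (hormonal/copper) as explanatory variables". The device covariate has two levels and none for a woman without a device. The population is set a line later: "Secondary analyses will be performed on all women with available data".

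Section 5, Variables and measures, describes what is stored: "The database will contain information on demographic variables, type of IUC inserted and sound measurement". No variable for the device chosen at entry is named.

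The same section says when the recommend question is put: "asked at the time of insertion and at the 3, 6 and 12 month follow up". It follows up all women by telephone or email and foresees never having had an insertion as a reason for non-use.

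On expected uptake, section 17.1 assumes that nearly every woman in the immediate arm receives a device and that fewer do in the delayed arm. Section 1 cites published evidence that "42 percent of women scheduled for delayed insertion after surgical abortion did not return for the follow up and IUC insertion".

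**The concern.** An ordinary logistic regression omits any woman with a missing covariate. If the covariate is the type inserted, a woman who never had an insertion has no value and leaves the model, even if she answered at follow-up. Whether a woman has an insertion depends strongly on the arm to which she was allocated; this is the trial's own hypothesis. The covariate would therefore remove a large part of one arm and little of the other, and the delayed arm would be judged only by women who came back and had a device placed.

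Acceptability is a stated secondary objective and part of a research question in section 5. For the primary outcome, section 17.1 expressly keeps women without an insertion in the analysis population. The acceptability model would undo that protection for this outcome.

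**Working it through.** **Inputs from the protocol**
- 720 women randomised 1:1, so 360 per arm (sections 5 and 17.1).
- IUC use at 6 months: 80% immediate, 60% delayed. Expulsion: at most 15% and 5% (section 17.1).
- Non-return for delayed insertion after surgical abortion: 42% (section 1).
- Loss to follow-up: 15% (section 17.1).

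The protocol gives no recommend rates. Those in step 5 are assumptions.

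**1. The plan's own figure.** There is none for acceptability, but the 80% and 60% used below are the inputs to the stated 109 per group. Two-sided alpha 0.05, 90% power, no continuity correction:

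n = [1.96 × √(2 × 0.70 × 0.30) + 1.2816 × √(0.80 × 0.20 + 0.60 × 0.40)]² / 0.20² = 108.2, rounded up to 109.

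The stated figure reproduces; power at 109 is 90.2%.

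**2. Never inserted, delayed arm.** If every non-user at 6 months was never inserted or had an expulsion, share inserted = use / (1 − expulsion).
- 0.60 / 0.95 = 63.2% inserted, 36.8% never inserted: 0.368 × 360 ≈ 133 women.
- With the 42% non-return figure: 0.42 × 360 ≈ 151 women.
- If 75% were inserted and removals explained the rest (an assumption): 0.25 × 360 = 90 women.

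**3. Never inserted, immediate arm.**
- All inserted: 0 women.
- Same formula: 0.80 / 0.85 = 94.1% inserted, 5.9% never inserted: about 21 women. Section 17.1 allows for some removals in this arm, so 21 is an upper value.

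**4. After loss to follow-up.** A woman without an answer is lost whatever the covariates. With 15% lost evenly:
- delayed: 0.85 × 133 ≈ 113 to 0.85 × 151 ≈ 128;
- immediate: 0 to 0.85 × 21 ≈ 18.

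If women who do not return for insertion also answer less often, fewer are dropped by the covariate.

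**5. Effect on the delayed-arm proportion.** Let r be the share inserted, a the recommend rate among inserted women and y the rate among never-inserted women. The rate among inserted women exceeds the rate in the whole arm by (1 − r) × (a − y). With r = 0.632 and a = 90% (assumed):

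| Assumed y | Whole arm | Inserted minus whole arm |
|---|---|---|
| 20% | 64.2% | +25.8 points |
| 60% | 79.0% | +11.0 points |
| 80% | 86.3% | +3.7 points |
| 90% | 90.0% | 0 |
| 95% | 91.8% | −1.8 points |

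The imbalance in who is dropped follows from the protocol's figures. The size and sign of the bias depend on y, which the protocol does not give.

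**The case against.** Section 17.1 says only type of IUC, not type inserted, and the sentence in section 5 is a short summary of the database. Women opt for an IUC before entry, and section 6.2 shows that the device class can be settled at eligibility: with a contraindication to the hormonal systems, "the woman may still choose a Cu-IUD and thereby enter the study". If the intended type is recorded before randomisation, the covariate exists for every woman and the problem goes away. This stands as a condition on the point. A reader might infer that type is recorded only for inserted women; the protocol does not say so. It is the natural reading, because no other device variable is named.

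The covariate is also not the only route to exclusion. The question put at the time of insertion omits never-inserted women whatever the model contains, and for such a woman the recommend item has a less clear meaning at follow-up. This stands too, and it limits the point to the 3-, 6- and 12-month answers. The preferred-timing item, though, can be answered by any randomised woman.

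A reader might further infer that the model overstates delayed-arm acceptability by a definite amount. That needs never-inserted women to be less favourable than inserted ones. The listed reasons for no attempt include heavy bleeding and unavailable staff, which need not mean dislike of the timing. If the bias does favour delayed insertion, it works against immediate insertion and is conservative for the non-inferiority objective. That is fair, but it depends on a sign that is not established, and a conservative bias can still hide a real result.

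Finally, the handling of missing covariates is commonly left to the SAP, which is not shown. The choice of covariate, however, is made in the protocol.

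**Conclusion.** The point holds conditionally. Unless the intended type is recorded at entry, the acceptability model conditions on a post-randomisation variable that is undefined for never-inserted women and drops them at 3, 6 and 12 months. On the protocol's assumptions this is about 37% to 42% of the delayed arm against 0% to 6% of the immediate arm. The delayed share rests on no removals in that arm (lower bound) or on a non-return figure taken from surgical abortion (upper bound); it falls if removals account for part of the non-use.

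The resulting comparison is not randomised. It probably favours delayed insertion, but the bias is zero if never-inserted women answer like inserted women and reverses if they are more favourable. No figure in percentage points can be attributed to the protocol. The point concerns one secondary outcome and leaves the primary analysis untouched. The change is worth making because it is cheap and removes an avoidable exclusion.

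**What to change.** In section 17.1, remove type of IUC from the main acceptability model. Fit group plus baseline variables (gestational stratum, site, age, parity) on all randomised women who answer at follow-up, and state that never-inserted women are included. Report device type only in a second model among inserted women, labelled as descriptive. Intended type may stay in the main model instead, but only if it is recorded before randomisation.

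The cost is a short edit to section 17.1. Dropping the covariate needs no new data; the intended-type option needs a field on the case report form if none exists. The downside is that the main model no longer estimates an effect of device type.

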### **Missing data**

Missing data on the primary outcome variable will cause the patient to be classified as a "drop-out".

## **18 Insurance**

The participants will be insured through the pharmacological insurance ("Läkemedelsförsäkringen") and the Swedish patient injury act ("Patientskadlagen").

## **19 Monitoring**

The study will continuously be monitored by an independent monitor from Danderyd Hospital's department of General Surgery. A minimum of three monitoring visits (study start, after first 5 recruited subjects and at study completion) will take place at each site. The monitor will check study specific procedures, including safety assessment, handling of study medication, data recording and source data verification. To assure the accuracy and completeness of the data recorded in the study the monitor will compare CRFs with medical records and any other relevant documentation during the on-site monitoring visits.

A source data list will be written for each site defining source data for this study.

Monitor and permitted staff from relevant authorities will be guaranteed access to print outs of patient records by the patients' agreement at the time of inclusion, and this will be documented in the informed consent form. Random checks will ensure that all relevant copies of records are printed.

## **20 Archive**

All study related documents will be kept in archive for at least 10 years after study completion according to national law.

## **21 Report and publishing**

- Within 90 days of completion of the study as a whole, the sponsor will report to the MPA and the RERB that the study is completed as stated in the protocol
- If the study will be ended and closed prematurely, the sponsor will report to the MPA and the RERB within 15 days. The reasons for the decision shall be reported
- The EU-common form "end of trial" shall be used and sent electronically to the MPA
- The sponsor will also send a summarizing report to the EudraCT database within 12 months after the study has been closed

- The results will be published as a scientific article in an international, peer-reviewed scientific journal

